6.2.2.2 Clinic visits (Visits 3, 4 and 5)

**Procedures and observations**

Pregnancy test	Urine pregnancy test
COPD exacerbation interview	
 
• Patient's reminder card (filled in by the patient) should be reviewed with the investigator.
 
• Telephone call(s) information since the last clinic visit should be reviewed.
 
 Please refer to the section 5.1.2.2
Patient's reminder card	Patients will be provided with a new card.

Assignment of trial drugs	Allocate the appropriate medication kits using IRT.
Dispense trial drug	Three new Respimat ® treatment boxes + 1 Respimat ® inhaler reserve are assigned. Enter the date of priming on the medication label of the Respimat ® . Record medication kit numbers in the eCRF.
Administration of trial drug	The patient will self-administer the trial drug (from the new assigned Respimat ® inhaler) under the oversight of the site staff.

Inhalation observance	Observance of the inhalation procedure. Give instructions on how to assemble and prime the Respimat ® inhaler at home.
Rescue medication	Provide sufficient rescue medication inhalers to cover the period between 2 clinic visits.
Collect trial drugs	All trial medications are to be collected. Compliance to be checked. Please refer to section 4.3 Treatment compliance.
Adverse events	All adverse events experienced since the previous visit will be reviewed and documented.

**Proprietary confidential information.**

© 2015 Boehringer Ingelheim International GmbH or one or more of its affiliated companies. All rights reserved.

This document may not - in full or in part - be passed on, reproduced, published or otherwise used without prior written permission.

Concomitant medication	Any changes in concomitant medications since the last visit will be reviewed and documented
Appointments	
Patients will be instructed to bring all issued trial medication (used/unused) and the rescue medication (used/unused) to the study site on the next scheduled clinic visit.
 
Schedule:
 
 
• J 4),0% &44,/0(5%0(K;%%<+&(%*
 
• 
 
• L%C( ./0/. 2/+/(8 5,0()+ '&(%@
 

### 6.2.2.3 Telephone contacts between clinic visits

[figure not shown]
Study sites will follow up patients and collect information by telephone interviews every 6-week ( $\pm$  7 days). A patient’s reminder card will be provided to assist their memory recall in terms of respiratory symptoms, COPD exacerbations, hospitalisation or interim health care visits, concomitant therapy.

At each telephone contact, the investigator or deputy will review with the patient any related COPD exacerbation information (new occurrence of exacerbation, respiratory symptoms, COPD exacerbation-related hospitalisation etc...) and will record it in the eCRF. If patients are hospitalised, the study site will be responsible for collecting and reviewing pertinent medical records so that an informed judgment can be made as to the primary cause for admission.

Relevant sources of information may include hospital records, telephone or written correspondence with primary physicians, discharge summaries, and death certificates.

Emphasis will be placed on the first diagnosis listed in the discharge summary in determining the primary cause for the hospital admission. In case of hospitalisation, patients will be encouraged to inform the study site prior to their regularly scheduled telephone interviews.

Details of all exacerbations will be captured in the source notes.

Proprietary confidential information.

© 2015 Boehringer Ingelheim International GmbH or one or more of its affiliated companies. All rights reserved.

This document may not - in full or in part - be passed on, reproduced, published or otherwise used without prior written permission.

### 6.2.3 End of treatment

#### 6.2.3.1 Visit 6/EoT

At the conclusion of the 52-week treatment period, the following information will be collected for all patients (these visit procedures also apply for a patient who is discontinuing trial medication before the end of the trial)-

[figure not shown]
#### Procedures and observations

Physical examination	Physical examination including measurements of systolic and diastolic blood pressure and pulse rate.
Haematology, serum chemistry laboratory tests	To be submitted to the central laboratory. (Fasted condition is not required).
Smoking status	To be reported.

[figure not shown]

COPD exacerbation interview	
 
• Patient's reminder card (filled in by the patient) should be reviewed with the investigator
 
• Telephone call(s) information since the last clinic visit should be reviewed.
 
 Please refer to the section 5.1.2.2
-----------------------------	--

Patient's reminder card	Patients will be provided with a new card.
-------------------------	--

Last trial drug administration	The last administration of the study medication from the Respimat ® inhaler that is in current use since no new Respimat ® treatment box will be assigned.
--------------------------------	--

Collect trial drug	All trial medications are to be collected. Compliance to be checked. Please refer to section 4.3 (Treatment compliance).
Rescue medication	Rescue medication will be issued to all patients to cover the period until the follow-up Visit.
Adverse events	All adverse events experienced since the previous visit will be reviewed and documented.

Proprietary confidential information.

© 2015 Boehringer Ingelheim International GmbH or one or more of its affiliated companies. All rights reserved.

This document may not - in full or in part - be passed on, reproduced, published or otherwise used without prior written permission.

Concomitant medication	Any changes in concomitant medications since the last visit will be reviewed and documented
Appointment	Patients will be instructed to bring all issued rescue medication (used/unused) at the follow-up visit. G.)%=-'%%>,"; ?-4 2/+(MN#&6+>(%6)/+(K@
Trial drug termination call	Please refer to the IRT manual

### 6.2.3.2 Premature discontinuation

The Visit 6/EoT visit should be performed instead of the scheduled trial visit at time of premature discontinuation (Please refer to [section 6.2.3.1](#)). Afterwards, the initiation of the survival and exacerbation information collection will be initiated.

The need for follow-up information (vital status and COPD exacerbation) should have been explained to patients prior to their participation in the trial and will be part of the written informed consent.

#### COPD exacerbation status collection

The collection of the COPD exacerbation status will be repeated every 6 weeks at the originally predicted clinic visits and telephone contacts until the predicted Visit 6.

Exacerbation contact information will be reported on the “COPD exacerbation check” eCRF. Exacerbation-related details will likewise recorded as an (S)AE and recorded in the COPD event eCRF, if applicable. In order to be able to provide COPD information, patients are strongly encouraged to use and complete the patient’s reminder card until the completion of the collection period.

Starting from the premise that COPD exacerbation and vital status collection should be timely aligned with the originally planned clinic visits and telephone contact. If the patient is not reachable during this period a second attempt is to be planned later (reason documented i.e: hospitalization, holiday, family events....).

**Proprietary confidential information.**

© 2015 Boehringer Ingelheim International GmbH or one or more of its affiliated companies. All rights reserved.

This document may not - in full or in part - be passed on, reproduced, published or otherwise used without prior written permission.

Vital status collection

Depending on the time of the patient’s withdrawal, the survival status collection will be scheduled as following:

- BEFORE Visit 4: 2 collection time points at the originally predicted visit 4 (26 weeks from Visit 2) and follow-up visit (52 weeks + 21 days from Visit 2)
- AFTER Visit 4: 1 collection time point at the originally predicted follow-up visit (52 weeks + 21 days from Visit 2).

The time interval of interest will be defined from the date of the Termination of Trial Medication (TTM) until their predicted follow-up visit.

If death occurs, the investigator will review the circumstances, including the relevant medical records to ascertain the most likely primary cause. Vital status information will be collected in accordance with national ethical and regulatory guidelines.

**6.2.4 Follow-up visit**

At the completion of the Visit 6 the follow-up visit should be performed in any case as described in the [flow chart](#).

A patient who is withdrawn from therapy should complete the follow-up visit 21 days later last treatment study visit (including the EOT assessments). Please refer to [section 6.2.3.2](#).

Physical examination	To be re-assessed ONLY in case of relevant findings at Visit 6 or at the last study treatment visit (in case of premature discontinuation)
Laboratory tests	To be re-assessed ONLY in case of relevant findings at Visit 6 or at the last study treatment visit (in case of premature discontinuation)
Pregnancy test	Urine pregnancy test
COPD exacerbation interview	
 
• Patient’s reminder card (filled in by the patient) should be reviewed with the investigator
 
• Telephone call(s) information since the last clinic visit should be reviewed.
 
 Please refer to the section 5.1.2.2
Rescue medication	To be collected
Adverse events	All adverse events experienced since the previous visit will be reviewed and documented.
Trial Completion	

### 6.2.5 Trial completion

#### For completed patient

The “Trial completion” definition takes into consideration the trial drug termination date (i.e., visit 6) completed 21 days later by the follow-up visit.

Trial completion page has to be filled-in when the patient has terminated the follow-up visit.

#### For discontinued patient

The “Trial completion” definition takes into consideration the premature trial drug termination date (i.e., prior to visit 6) completed 21 days later by the follow-up visit.

Trial completion page has to be filled-in when the patient has terminated the follow-up visit. Please refer to [section 6.2.3.2](#).

## 7. STATISTICAL METHODS AND DETERMINATION OF SAMPLE SIZE

### 7.1 STATISTICAL DESIGN - MODEL

This is a randomised, double-blind, active-controlled parallel group, phase IIIb study. The primary objective of this study is to evaluate the effect of once daily treatment of tiotropium 5 µg + olodaterol 5 µg FDC delivered by the Respimat® inhaler on COPD exacerbation as compared with 5 µg tiotropium delivered by the Respimat® inhaler in patients with severe to very severe COPD. Each patient will stay in the trial for 52 weeks and will be followed up for COPD exacerbation if dropped out earlier. Vital status will be collected over the entire study period (52 weeks + 21 days follow-up).

### 7.2 NULL AND ALTERNATIVE HYPOTHESES

The effect of tiotropium + olodaterol FDC on COPD exacerbation will be assessed by testing the rate ratio for annual rate of moderate/severe COPD exacerbation and hazard ratio for moderate/severe COPD exacerbation between T+O FDC and Tio 5 in the following hypothesis testing hierarchy:

9.  $H_{10}$ : the annualised rate of moderate to severe COPD exacerbation is equal between T+O 5/5 and Tio 5

vs.

$H_{11}$ : the annualised rate of moderate to severe COPD exacerbation is different between T+O 5/5 and Tio 5.

10.  $H_{20}$ : the survival distribution for the onset of the first moderate to severe COPD exacerbation is equal for T+O 5/5 and Tio 5

vs.

$H_{21}$ : the survival distribution for the onset of the first moderate to severe COPD exacerbation is different for T+O 5/5 and Tio 5

This hypothesis testing strategy ensures that the overall type I error is protected at two-sided 0.01 level.

### 7.3 PLANNED ANALYSES

#### 7.3.1 Primary analyses

The primary analysis includes all randomised patients who are documented to have received any dose of study medication, i.e., the primary analysis is performed using the treated set.

The primary endpoint, i.e., annualised rate of moderate to severe COPD exacerbation will be analysed using a negative binomial model including the fixed, categorical effect of treatment

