### 3.3 SELECTION OF TRIAL POPULATION

It is widely accepted that a COPD exacerbation increases the risk of the occurrence of future COPD exacerbations and that the frequency of exacerbations increases with progression of COPD. The trial will recruit patients with severe lung function impairment and a history of occurrence of moderate to severe treated COPD exacerbations, as these patients are known to have greater likelihood of having a re-occurrence of COPD exacerbation. The eligibility criteria employed in the study will allow enriching the patient population by ensuring the recruitment of patients prone to exacerbations.

This trial will be conducted worldwide and the distribution of patients between the countries will be dependent on the access to suitable patients as well as the operational feasibility of performing the trial in the country. It is anticipated that each site will enrol an average of 10 to 12 patients.

An estimated total of 7800 patients randomised will be necessary to assess the primary endpoint “Annualised rate of moderate to severe COPD exacerbation during the treatment period”. Between Visit 1 and Visit 2, a low screen failure rate of 5% is foreseen due to the short screening period and, therefore, a lower likelihood for the enrolled patient to experience a new COPD exacerbation before the randomisation visit.

A log of all patients included into the study (i.e. having given informed consent) will be maintained in the ISF at the investigational site irrespective of whether they have been treated with investigational drug or not.

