### 7.3.2 Secondary analyses

For the key secondary endpoint, i.e., time to the onset of the first moderate to severe COPD exacerbation, as well as other time to event endpoints (see [Section 5.1.1](#)), a Cox's proportional hazard model will be used to estimate the hazard ratio and the corresponding 99% confidence intervals, while log-rank test will be used to obtain the p-value for testing the survival curves. For other annualised rate of event endpoints (see Section 5.1.1), the same negative binomial model as specified for the primary endpoint will be used.

For all efficacy analyses including time to all-cause mortality the treated set (on-treatment + 1 day) will be used.

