**Proprietary confidential information.**

© 2015 Boehringer Ingelheim International GmbH or one or more of its affiliated companies. All rights reserved.

This document may not - in full or in part - be passed on, reproduced, published or otherwise used without prior written permission.

Table 7.6: 1 Sample size estimations for annualised rate of moderate to severe COPD exacerbation under different dispersion parameters with 2-sided type I error rate of 0.01, 90% power, annual rate of 0.85 in Tio 5 and rate ratio = 0.88

Annual Rate in Tio 5 (r 1 )	Annual Rate in T+O FDC (r 2 )	r 2 /r 1	Dispersion Parameter	N per arm	Average exposure (months)	Total exposure adjusted for 15% loss of information (patient – years)	Power (after adjusting 15% loss of information in patient-years)
0.85	0.748	0.88	0.625 (SPARK)	3427	12	2913	85.8%
0.85	0.748	0.88	0.7	3563	12	3029	86.0%
0.85	0.748	0.88	0.8	3745	12	3184	86.2%
0.85	0.748	0.88	0.9	3927	12	3338	86.4%

The above calculation is based on the formulas in Zhu and Lakkis [P14-09564] and was calculated using the validated software package R. A sample size of 3900 patients per arm will give a power between 90% to 94% under different dispersion parameters to detect a rate ratio of 0.88 between T+O FDC and Tio 5 in the annualised rate of moderate to severe COPD exacerbation assuming the annual rate in Tio 5 is 0.85 and two-sided type I error rate of 0.01. After adjusting for a 15% loss of information in patient-years and the same assumptions as above, a sample size of 3900 patients per arm will give a power between 86.1% to 90.6%

Assuming the proportion of patients who had at least one moderate to severe COPD exacerbation within 1 year in the Tio 5 arm is 0.65, a hazard ratio between T+O FDC and Tio 5 of 0.88, a two-sided type I error rate of 0.01 and power of 90%, the estimated sample size for time to the first moderate/severe COPD exacerbation is 2915 patients per arm (using nQuery Advisor 7.0). A sample size of 3900 patients per arm will give a power of 97% using the same assumptions.

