### **6.5 POOLING OF CENTRES**

This section is not applicable because centre/country is not included in the statistical model.

[figure not shown]

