## **7.2 CONCOMITANT DISEASES AND MEDICATION**

Concomitant diseases and medication are collected by checkbox and will be summarized by treatment using descriptive statistics. For medical history, displays will be created for each: past, ongoing or recurring events as recorded at baseline. The following concomitant diseases and medications will be included:

- Medical history [N (%)] (Metabolic disorders [diabetes mellitus, hyper-/dyslipidaemia], psychiatric disorders [anxiety, depression], renal and urinary disorders [prostatic disorder, urinary retention, urinary tract infection, renal impairment (renal failure)], cancer [treated basal cell carcinoma, squamous cell skin cancer], cardiac arrhythmia [supraventricular tachyarrhythmia, atrial fibrillation/flutter, ventricular tachyarrhythmia, palpitations, bradyarrhythmia, QT prolongation], cerebrovascular disorders/stroke [haemorrhagic cerebrovascular conditions, ischaemic cerebrovascular conditions, transient cerebrovascular event (TIA)], other cardiovascular disease [hypertension, hypotension, aneurysm, syncope, myocardial infarction (MI), other ischaemic heart disease (non-infarction, angina pectoris), cardiac arrest, cardiac failure class (New York Heart Association (NYHA) failure classification)], including number of COPD exacerbations or worsening episodes in the last year that were treated with steroids or antibiotics, number of COPD exacerbations in the last year that were associated with hospitalization, CAT
- Concomitant therapy (CT) at baseline [N,(%)]
  - Pulmonary classes (as specified on case report form)
  - Cardiac classes (as specified on case report form)
  - Metabolic disease, psychiatric disease (as specified on case report form)
- CT during treatment period [N (%)], if indicated to have been used for one day during randomized treatment period (Visit 2 through termination of trial medication will be summarized together. A separate display will be generated summarizing from the end of treatment until the 21 day follow-up visit.)

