## **7.4 PRIMARY ENDPOINT**

### Primary Analysis

As stated in section 7.3.1 in the revised CTP: “The annualized rate of moderate to severe COPD exacerbation will be analyzed using a negative binomial model including the fixed, category effect of treatment as well as the logarithm of the treatment exposure as an offset. [...] Moderate to severe COPD exacerbations occurring within 1 day (24 hours) after the last drug administration date, are included in the primary analysis”.

See [section 6.9](#) for calculation of observed rate.

Annualized rates of moderate to severe COPD exacerbations will be tested for equivalence between the two treatment groups T+O 5/5 and Tio 5. The hypothesis (H) test is:

$$H_{10}: RR = 1$$

vs.

$$H_{11}: RR \neq 1,$$

where  $RR = \frac{\lambda_{(T+O)}}{\lambda_{(Tio)}}$  and  $\lambda_{Tio}$  is the annualized rate for the patients in the Tio 5 group and  $\lambda_{T+O}$  is the annualized rate for the patients in the T+O 5/5 group and RR is the rate ratio between the two groups.

[figure not shown]
The hypothesis test will be evaluated using a two-sided  $\alpha=0.01$ . Ninety-nine (99)% confidence intervals will be obtained. Type III sums of squares will be produced.

The following SAS® code for the negative binomial model will be used:

```
proc genmod data=exac_negbin;
  class trt;
  model evtnum=trt/noint dist=negbin link=log offset=logdurs type3
  alpha=0.01;
  lsmeans trt/cl diff exp alpha=0.01;
run;
```

where TRT=treatment group and LOGDURS=log(exposure) as described in [section 6.9](#). The OFFSET=LOGDURS is used to account for different exposure, or observation periods per subject.

The primary analysis will be an actual treatment analysis performed on the treated set (TS) (see [section 6.3](#)). The exacerbation events will be only counted in this analysis if they occurred during the actual treatment period (see [section 6.1](#)).

[Section 9.1](#) details additional rules applied to the analysis of the primary endpoint.

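### The primary negative binomial model adjusts for nothing but treatment, although prior-year exacerbation counts are collected; prespecified adjustment would buy a modest gain in precision at no data cost

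*Protocol*

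**What the plan says.** Protocol 7.3.1 states that the annualised rate of moderate to severe exacerbations is "analysed using a negative binomial model including the fixed, categorical effect of treatment", with the logarithm of exposure as offset. The code in SAP 7.4 agrees: "model evtnum=trt/noint dist=negbin link=log offset=logdurs type3". Treatment is the only regressor. SAP 6.5 adds that "centre/country is not included in the statistical model". Protocol 7.3.2 carries the model over to the other rate endpoint, the rate of exacerbations leading to hospitalisation: "the same negative binomial model as specified for the primary endpoint will be used".

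On the predictor, Protocol 3.3 says: "It is widely accepted that a COPD exacerbation increases the risk of the occurrence of future COPD exacerbations". It uses this to justify recruiting patients prone to exacerbations. SAP 7.2 lists two baseline counts for descriptive display: the "number of COPD exacerbations or worsening episodes in the last year that were treated with steroids or antibiotics" and the "number of COPD exacerbations in the last year that were associated with hospitalization". The visible text uses neither in a model and gives no reason for leaving them out.

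On power, Protocol 7.6 reports that after a 15% loss of patient-years "a sample size of 3900 patients per arm will give a power between 86.1% to 90.6" per cent, across dispersions of 0.9 down to 0.625.

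**The concern.** The plan relies on exacerbation history to select patients and then ignores it in the analysis. In a negative binomial model, between-patient variation that a baseline covariate could explain stays in the dispersion parameter and widens the interval for the rate ratio. The design input was 90% power at two-sided 0.01. By the protocol's own figures, power after information loss falls below that at the upper end of the dispersion range. A covariate already in the database could recover part of the difference without enrolling anyone. The hospitalisation-rate model has the same gap, although a prior-year hospitalised count is collected.

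Validity, type I error and the meaning of the estimate are not at stake. Only precision is.

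**Working it through.** **Inputs from Protocol 7.6.** Control rate 0.85 per year, test rate 0.748 (ratio 0.88), 3900 per arm, two-sided alpha 0.01 (z = 2.576), dispersion k from 0.625 to 0.9, mean exposure 0.85 year after the 15% loss.

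**Reproducing the plan.** The variance of the log rate ratio is V/n, with n patients per arm and

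V = 1/(0.85 × 0.85) + 1/(0.748 × 0.85) + 2k = 1.384 + 1.573 + 2k.

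Power = Φ(|ln 0.88| × √(3900/V) − 2.576), with |ln 0.88| = 0.1278.

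- k = 0.9: V = 4.757, power 86.1%.
- k = 0.625: V = 4.207, power 90.6%.

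Both match the protocol. With a full year of exposure, the same formula returns the tabulated sample sizes (3427, 3563, 3745, 3927) to within one patient.

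**Adding the covariate.** The documents give neither its distribution nor its strength. I assume that a share p = 0.4 of patients have two or more prior-year events, at R times the rate of the others.

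- Mean relative rate: m = 1 − p + pR.
- Spread due to the covariate: c = (1 − p + pR²)/m².
- Residual dispersion, holding total dispersion at k: k_r = (k + 1 − c)/c.
- Information per patient in an arm: the sum over the two covariate levels of (share) × μ/(1 + k_r μ), where μ is the expected count at that level.
- V is the sum over arms of 1/information.

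Example, k = 0.9 and R = 2.0:

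- m = 1.4, c = 2.2/1.96 = 1.1224, k_r = 0.693.
- The control mean is 0.85 × 0.85 = 0.7225, so the two levels have means 0.516 and 1.032, and the information is 0.228 + 0.241 = 0.469.
- The test arm gives 0.430.
- V = 1/0.469 + 1/0.430 = 4.457 (from unrounded values), a fall of 6.3%, and power is 88.6%.

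| k | R | k_r | Fall in variance | Power, unadjusted → adjusted |
|---|---|---|---|---|
| 0.9 | 1.5 | 0.824 | 2.3% | 86.1% → 87.0% |
| 0.9 | 1.75 | 0.759 | 4.3% | 86.1% → 87.8% |
| 0.9 | 2.0 | 0.693 | 6.3% | 86.1% → 88.6% |
| 0.625 | 1.5 | 0.560 | 2.3% | 90.6% → 91.3% |
| 0.625 | 1.75 | 0.505 | 4.3% | 90.6% → 92.0% |
| 0.625 | 2.0 | 0.448 | 6.4% | 90.6% → 92.6% |

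**Sensitivity at k = 0.9.** Moving p between 0.3 and 0.5 gives a fall of 2.2% to 2.3% at R = 1.5 and 5.7% to 6.5% at R = 2.0. At R = 1.25 (p = 0.4) the fall is 0.7%, worth 0.3 power points.

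**Simulation under the same assumptions** (100 trials per scenario, 3900 per arm, gamma frailty, 30% of patients dropping out uniformly). Mean standard error of the log rate ratio, unadjusted → adjusted, with the fall in variance as 1 minus the squared ratio of the two:

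- k = 0.9, R = 1.5: 0.03543 → 0.03511, 1.8%.
- k = 0.9, R = 2.0: 0.03526 → 0.03431, 5.3%.
- k = 0.625, R = 1.5: 0.03332 → 0.03298, 2.0%.
- k = 0.625, R = 2.0: 0.03318 → 0.03214, 6.2%.

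The estimated rate ratio barely moved: means of 0.877 unadjusted against 0.876 adjusted in one comparison, and 0.884 both ways in another.

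**Second simulation, honouring the entry rule.** Every patient had at least one prior event, the count entered as 1, 2 or 3 and above, and the correlation between past and future frailty was 0.25 to 0.75. The variance fell by 0.6% to 5.6%. This used only eight trials per setting, so it shows order of magnitude.

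**The case against.** The strongest reply is that nothing is broken. The unadjusted model is valid under randomisation, the protocol and SAP agree with each other, and the sample size was computed for exactly this model. All of that stands.

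The size of the gain is not in the documents. It rests on an assumed prevalence and rate ratio, the simulated gains sit slightly below the analytic ones, and a weak covariate yields almost nothing. Protocol 3.3 speaks of having had an exacerbation, and inclusion criterion 4 already requires one of every patient. No passage says that two or more against one separates risk within the enrolled population. This also stands, and it is why the gain is given as a range that reaches close to zero.

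The power shortfall should not be overplayed. The 90% was the input before information loss, the protocol discloses the figures after loss, and at dispersion 0.625 power is still 90.6%. At 0.9, restoring 90% would need V to fall from 4.757 to about 4.28, roughly 10%. No scenario above reaches that, so the recovery is partial.

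The key secondary log-rank test would remain unadjusted. This mismatch does not affect the validity of the testing hierarchy.

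Finally, parts of the documents are not visible (the content of SAP section 4, SAP 6.4 and Protocol 7.3.5), so a supportive adjusted analysis may exist. That would not change the primary model, which is fully visible. None of these points shows a harm or a material cost from adjusting.

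**Conclusion.** The concern holds, as a missed efficiency and not an error. If 40% of patients have two or more prior-year events at 1.5 to 2.0 times the rate of the rest, adjustment gains 0.9 to 2.5 power points at dispersion 0.9 and 0.7 to 2.0 points at 0.625. Those assumptions are mine. The gain shrinks to about 0.3 points at dispersion 0.9 if the ratio is only 1.25. The rate ratio itself is essentially unaffected. The change is worth making because it is nearly free, not because the trial fails without it. Confidence is medium, since the strength of the covariate in this population is unknown.

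**What to change.** Before unblinding, amend Protocol 7.3.1 and SAP 7.4 as follows.

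- Add the prior-year exacerbation count (0 or 1 versus 2 or more) as a fixed covariate in the primary model.
- State whether the count uses the steroid- or antibiotic-treated events alone or also the hospitalised ones. SAP 7.2 does not say whether its two counts overlap.
- Keep 0 in the low category. SAP Table 6.2:1 does not exclude patients who fail inclusion criterion 4, so some may have no prior event.
- Give patients without a recorded count their own missing category, so that the treated set is unchanged.
- Optionally add any prior-year hospitalised exacerbation (yes/no), chiefly in the hospitalisation-rate model.
- Report the unadjusted model as a sensitivity analysis.

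The cost is an amendment to the final SAP and to the protocol wording, and one or two extra parameters plus the missing category in about 7800 patients. No new data are needed. If the sponsor prefers the unadjusted model, a sentence giving the reason would be enough.
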